An optional part of the study protocol, a subcohort of at least 200 patients (funds allowing) will be offered a routine 30-day post-RP screening lower extremity Duplex ultrasound to assess for DVT at Johns Hopkins for patients willing to travel to Johns Hopkins to obtain the ultrasound in this time frame. Patients are not required to obtain this screening ultrasound, but initial randomization will be stratified by whether patients opt to undergo ultrasound (and robotic vs. open surgery) to ensure study arms are balanced. In other words, patients willing to undergo ultrasound will be identified before randomization. All patients, regardless of whether they undergo ultrasound, will be assessed for all primary outcomes as described. For the subset of patients who obtain the ultrasound, it will be used to assess the secondary outcome of any VTE (asymptomatic or symptomatic). The outcome of any VTE will be tabulated based on the results of the screening ultrasound and any report of a symptomatic VTE episode (assessed by call at 30 days as described above). Stratified randomization is outlined in Figure 1. Written informed consent includes a plan to inform the patient and their primary physician of the results of the ultrasound and any incidental findings. Costs for the screening ultrasound obtained as part of the study will be covered by the study. Symptoms prompting a recommendation for evaluation to rule out DVT or PE (appropriate diagnostics/imaging to be determined by evaluating physician) will include:

1. Persistent unilateral or bilateral lower extremity edema
2. Persistent calf pain or cramping
3. Persistent or new chest pain
4. Persistent or new shortness of breath that started suddenly or worsens with exertion
5. Productive cough with bloody sputum
6. Fever and/or tachycardia without any known source of infection
7. Any other clinical concern for DVT or PE

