The primary efficacy outcome will be the incidence of symptomatic VTE. The primary safety outcomes will include three separate measures of incidence of symptomatic lymphocele, incidence of symptomatic hematoma, or major bleeding within 30 days after surgery. The secondary outcomes (all regarded separately) will be estimated blood loss from surgery, total surgical drain output after surgery (for patients with surgical drains), the overall incidence of VTE (asymptomatic or symptomatic) determined from the subcohort undergoing lower extremity Duplex screening ultrasound, and surveillance bias (measured by use of postoperative diagnostic imaging, either as inpatient or within 30 days from surgery). Two planned interim analyses will be conducted as outlined in the study statistics section with early stopping rules due to adverse events or demonstrated futility.

[figure not shown]

Figure 1. Diagram of plan for stratified randomization of patients to arms and outcomes assessed.

b. Study duration and number of study visits required of research participants.

The study protocol will be largely implemented during routine visits required of all RP patients (described above) with the addition of a visit specifically for screening lower extremity Duplex for eligible patients as part of the run-in described above. Patients will be contacted by phone around 30 days after surgery to tabulate the primary and secondary outcomes. Patients may initiate contact before this point if they wish to report concerns or diagnosis of VTE. Any events that occur after 30 days and are reported by patients in an unsolicited fashion will be documented, but they will not be included as part of the primary outcome. There will be no planned contact initiated by the study team with patients after 30 days except to confirm documentation of VTE events that occurred up to 30 days from surgery due to symptoms or discovered on screening lower extremity Duplex ultrasound. Patients reporting symptoms concerning for VTE at or before the 30 day mark who are diagnosed within 2 weeks of reporting symptoms (even if after the 30 day mark) will be included as symptomatic VTE events for the primary outcome.

c. Blinding, including justification for blinding or not blinding the trial, if applicable.

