Randomization by blocks will be used, with stratification for type of surgery (robotic/laparoscopic vs. open) and subcohort membership (agrees to 30 day ultrasound/does not agree to 30 day ultrasound). Currently at Johns Hopkins approximately 40% of RPs are performed open, with the remainder robotic or laparoscopic, and the subcohort is planned to include 200 patients. Note that patients are randomized within each of the 4 subgroups formed by cross classification of these 2 strata, not randomized to the strata. Therefore, anticipated sizes of the 4 strata are

1. open RP/subcohort member, n=80
2. open RP/not subcohort member, n=186
3. robotic RP/subcohort member, n=120
4. robotic RP/not subcohort member, n=280

Because the above numbers are subject to variability in the choice of surgical approach, randomization lists will increase the number in each of the surgical categories by 20%, i.e. 320 and 480 random assignments will be generated for open and robotic surgeries, respectively. An undisclosed block size will be used to prevent any ability to predict next treatment assignment. The randomization lists will be generated by [name] using SAS PROC PLAN. Although this uses a pseudorandom number generator it has the advantage of reproducibility when the same seed is used. [name] will maintain the randomization list, password protected, on a remote drive maintained by the Department of Urology, and will provide the random assignment to the study coordinator as each patient is enrolled. Because surgery dates are scheduled weeks in advance, there is no concern about inability to access the randomization list. A biostatistician who works for [name] and is not otherwise connected to this trial will also have access to the random assignments and can provide them to the study coordinator in the unlikely event that [name] is unavailable. Only [name] and the biostatistician ([name]) have access to the remote drive.

b. Primary outcome variable.

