The secondary outcomes (all regarded separately) will be estimated blood loss from surgery, total surgical drain output after surgery (for patients with surgical drains), the overall incidence of VTE (asymptomatic or symptomatic) determined from the subcohort undergoing lower extremity Duplex screening ultrasound, and surveillance bias (measured by use of postoperative diagnostic imaging). Estimated blood loss will be recorded from the anesthesia data report from surgery. Total surgical drain output will be recorded based on ins and outs flowsheets routinely recorded by nurses when emptying drains. Surveillance bias will be determined by recording the type and frequency of postoperative imaging performed while a patient is in the hospital or within 30 days of surgery after discharge.

The overall rate of VTE will only be determined for patients in the subcohort. The asymptomatic VTE will be determined based on the results of the screening lower extremity Duplex ultrasound for asymptomatic DVTs. The overall rate of VTE will be determined by adding the number of asymptomatic VTE events to the number of symptomatic VTE events experienced in the subcohort.

d. Statistical plan including sample size justification and interim data analyses.

Pharmacologic VTE prophylaxis can be expected to prevent between 67% to 75% of DVTs [33]. Given the lowest expected primary outcome event rate will be for VTE, the trial sample size will be based on a power of 80% ($\beta=0.2$) and one-sided α of 0.05 for prevention of post-operative VTE with pharmacologic prophylaxis reducing the rate from 5% to 1.5%. Including two interim analyses of the primary endpoint as outlined in the Interim Analyses section below, the total sample size needed will be 666 (333 per treatment arm) based on 2000 simulations for 82% power (exact α -spending and futility boundaries are outlined below). As mentioned above, the primary efficacy analysis will compare symptomatic VTE rates at the 30-day follow-up for all patients. Secondary analyses will be conducted to compare secondary outcomes between treatment arms at the completion of the study as well. It is expected that during full-time patient enrollment, the study would require about 2 years to accrue patients assuming 50% enrollment.

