Two planned interim analyses of the primary endpoint will be conducted, after one-third and two-thirds of patients have undergone RP. Early stopping for efficacy or futility will be assessed at these time points. Details are provided below under Interim Analyses.

Statistical analyses: The treatment and control groups will be compared to identify any imbalance after randomization in relevant characteristics. Comparisons will include factors such as age, race, BMI, comorbidities, prostate volume, tumor stage, operative time, and blood loss. Discrete factors will be compared with chi-squared test, and continuous factors will be compared with t-test or Wilcoxon ranksum test if data do not conform to a Gaussian distribution. Analysis of the primary outcome (symptomatic VTE) will compare 30 day post-RP rates between the treatment and control groups, using chi-squared test. Logistic regression will be used if adjustment is required for any potential confounders not balanced by randomization, with the treatment effect estimated by the odds ratio and 95% confidence interval. Similar comparison of univariate rates, and adjusted odds ratios will be used for the 3 primary safety endpoints (lymphocele, hematoma, occurrence of major bleeding), and for the secondary outcome of any VTE (restricted to patients who undergo the 30 day lower extremity Duplex ultrasound). Secondary endpoints with a continuous metric (blood loss, surgical drain output, number of imaging tests (surveillance bias)) will be compared in univariate fashion using t-test or Wilcoxon ranksum, and adjusted analyses will use linear regression. Note that analysis of drain output is confined to patients with drains placed, so it is not protected by the randomization, potentially limiting interpretability if the number of patients is small and confounding factors are not well balanced. All analyses of primary and secondary outcomes will be based on intention to treat (ITT). Per protocol analyses will also be conducted, but treatment success will be based on ITT.

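### Any VTE is analysed only in patients who attend the day-30 scan, although the subcohort is fixed by agreement before randomisation, so known VTE events can drop out of this secondary outcome

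*Combined protocol and SAP*

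**What the plan says.** Two definitions of the any-VTE set run through the protocol.

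**Fixed before randomisation.** Section 7a stratifies by "subcohort membership (agrees to 30 day ultrasound/does not agree to 30 day ultrasound", and Section 4a says that willing patients are identified before they are randomised. Section 7c states "The overall rate of VTE will only be determined for patients in the subcohort" and obtains the overall rate "by adding the number of asymptomatic VTE events to the number of symptomatic VTE events experienced in the subcohort". Section 4a tabulates any VTE "based on the results of the screening ultrasound and any report of a symptomatic VTE episode".

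**Fixed by later attendance.** Section 7d gives the analysis "for the secondary outcome of any VTE (restricted to patients who undergo the 30 day lower extremity Duplex ultrasound". Other sections partly echo this: Sections 4a and 7c both use the phrase "determined from the subcohort undergoing lower extremity Duplex screening ultrasound", and Section 4a adds "For the subset of patients who obtain the ultrasound, it will be used to assess the secondary outcome of any VTE".

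Four other provisions bear on the point. Section 4a leaves the scan optional. Section 7b counts a death attributed to clinically suspected VTE as symptomatic VTE without imaging, subject to confirmation if an autopsy is done. Section 4f lets patients with VTE be treated locally. Section 7d says that all primary and secondary outcomes are analysed by ITT.

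**The concern.** Agreement to the scan is a baseline characteristic and a randomisation stratum, so a comparison among those who agreed is protected by randomisation. Attendance comes after randomisation and can depend on the outcome. A patient who dies before day 30 cannot be scanned, and one who has been diagnosed and is being treated near home may not travel back. The literal rule in Section 7d then removes patients because they had the event that the outcome is meant to count.

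Heparin is open label after surgery, so attendance could also differ by arm. Section 7d warns that drain output, another subset formed after randomisation, is not protected by the randomisation. It gives no such warning for any VTE.

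At stake are the rates, the risk difference and the number of events for any VTE and, under some conditions, the ratio measures.

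**Working it through.** **Plan figures.** The plan gives no rate or power for any VTE, so there is no stated figure to reproduce. The 82% power in Section 7d concerns symptomatic VTE in all 666 patients and is not in question. From the documents:
- Subcohort of 200 (Section 7a: 80 open + 120 robotic), taken as 100 per arm.
- Symptomatic VTE 5% versus 1.5% (Section 7d), so 5.0 versus 1.5 expected events. The relative reduction is 1 − 1.5/5 = 70%, inside the 67% to 75% that Section 7d cites for DVTs.

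**Assumptions.** Silent DVT is 5 per 100 controls. Every patient without symptomatic VTE is scanned. A share *u* of symptomatic patients is not scanned.

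**Formula.** With S symptomatic and A silent cases per 100, the scanned-only rate is [S(1 − u) + A] / [100 − uS].

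*Case A: heparin also cuts silent DVT, 5% to 1.5%*

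| u, both arms | Control | Heparin | Difference (points) | RR | OR |
|---|---|---|---|---|---|
| 0 | 10/100 = 10.00% | 3/100 = 3.00% | 7.00 | 0.300 | 0.278 |
| 50% | 7.5/97.5 = 7.69% | 2.25/99.25 = 2.27% | 5.43 | 0.295 | 0.278 |
| 100% (extreme) | 5/95 = 5.26% | 1.5/98.5 = 1.52% | 3.74 | 0.289 | 0.278 |

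The odds ratio does not move because the non-events (90 and 97) are untouched and the events shrink by the same factor in both arms: (3/97)/(10/90) = (2.25/97)/(7.5/90) = 0.278. Expected events fall from 13 to 9.75 to 6.5.

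*Case B: heparin has no effect on silent DVT, 5% in both arms*

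| u | Control | Heparin | Difference (points) | RR | OR |
|---|---|---|---|---|---|
| 0 | 10/100 = 10.00% | 6.5/100 = 6.50% | 3.50 | 0.650 | 0.626 |
| 25% both | 8.75/98.75 = 8.86% | 6.125/99.625 = 6.15% | 2.71 | 0.694 | 0.674 |
| 50% both | 7.5/97.5 = 7.69% | 5.75/99.25 = 5.79% | 1.90 | 0.753 | 0.738 |
| 100% both (extreme) | 5/95 = 5.26% | 5/98.5 = 5.08% | 0.19 | 0.964 | 0.963 |
| 50% control only | 7.69% | 6.50% | 1.19 | 0.845 | 0.834 |
| 50% heparin only | 10.00% | 5.79% | 4.21 | 0.579 | 0.553 |

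One-arm loss biases Case A too: 50% in controls only gives 3.00/7.69 = RR 0.39, and in heparin only 2.27/10.00 = RR 0.23, against 0.30.

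**Range for the silent rate (Case B).** The screening studies in Section 3 found DVT in 2/245 = 0.8% and 18/109 = 16.5% (the protocol prints 16.9%). They scanned within a week and on day 3, so they are only a rough guide to day 30.
- At 1%, RR goes from 2.5/6.0 = 0.42 to (1.75/99.25)/(3.5/97.5) = 0.49 at 50% loss.
- At 16.5%, RR goes from 18.0/21.5 = 0.84 to (17.25/99.25)/(19.0/97.5) = 0.89.

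**Non-attendance unrelated to events.** If 20% of everyone is unscanned at random, Case B gives 8/80 = 10.0% versus 5.2/80 = 6.5%. The rates are unchanged and only precision is lost.

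**The case against.** The strongest objections, and what stands of each:

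- **The scanned-only wording is not confined to Section 7d.** This stands. Sections 4a and 7c partly share it, so a reader who infers that one stray sentence contradicts an otherwise uniform protocol goes too far. Nor is it right that the plan is silent on unscanned opt-in patients: read literally, Section 7d excludes them. The two definitions still conflict.
- **A reader might infer that the rule pulls the heparin effect toward the null.** The documents do not support that as a general result. Section 7d's 67% to 75% is stated for DVTs without limiting it to symptomatic ones, and under a proportional effect with equal loss the plan's own measure, the odds ratio, does not change. With 67% or 75% applied to silent DVT, it moves only from 0.29 to 0.31, or from 0.25 to 0.23, between no loss and total loss.
- **The loss rates are hypothetical.** This stands. Opt-in patients are those willing to travel, and Section 11 covers the study scan even after earlier positive imaging. That partly mitigates the problem for survivors, although the sentence is worded for asymptomatic patients and cannot help with deaths. Deaths should be few: the 0.4% PE rate in Section 3 (32/8381, fatal or not) implies 0.8 in 200 patients.
- **The shift is small against the noise.** At 10% versus 6.5% the standard error of the difference is √(0.10×0.90/100 + 0.065×0.935/100) = 3.9 points. The Case B shifts at 25% and 50% loss (0.8 and 1.6 points) are about 0.2 and 0.4 standard errors. True, but imprecision is no reason to discard known events.
- **No event is lost to the trial.** Correct. The primary outcome counts symptomatic VTE in all patients.
- **Section 4f's inclusion sentence concerns dose compliance, not scan attendance.** Fair. The firmer conflict is with the ITT sentence in Section 7d.

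**Conclusion.** The concern holds as a faulty stated rule for one secondary outcome in about 200 patients. Followed literally, Section 7d selects on attendance after randomisation, against the plan's own ITT statement and its construction of the endpoint in Section 7c. Exclusion is certain for an opted-in patient who dies of VTE before the scan, and only possible for one treated locally.

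The size cannot be fixed from the documents. Under a proportional heparin effect and equal loss, the cost is a smaller risk difference (7.0 to 5.4 points at 50% loss) and fewer events, with the odds ratio intact. The ratio is attenuated if heparin spares silent DVT less than symptomatic VTE (RR 0.65 to 0.75 in Case B at 50% loss), and biased in either direction if loss differs by arm (RR 0.85 or 0.58 in Case B). All of these rest on assumed attendance and silent-DVT rates. The primary endpoint, sample size and alpha are unaffected. The change should be made, but the trial's main conclusion does not depend on it.

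**What to change.** Reconcile Sections 4a, 7a, 7c and 7d on one definition:

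1. The any-VTE set is all randomised, operated patients in the opt-in strata, with one yes/no outcome per patient.
2. Every symptomatic VTE, including VTE deaths as defined in Section 7b, counts whether or not the patient was scanned.
3. Unscanned patients without a symptomatic event stay in the set, with only their silent component treated as missing.
4. Scan attendance is reported by arm, and the scanned-only result is kept as a sensitivity analysis.

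Best/worst-case bounds or imputation are optional.

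The cost is wording only, since the 30-day call already collects symptomatic events from all patients. The drawback is a small and imprecise missing-data step. In Case B with an assumed 10% of patients without symptomatic VTE unscanned, the bounds for control run from (5 + 4.5)/100 = 9.5% to (9.5 + 9.5)/100 = 19.0%. For heparin they run from (1.5 + 4.5)/100 = 6.0% to (6.0 + 9.85)/100 = 15.9%.

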Specific aims: Does the use of perioperative pharmacologic agents (subcutaneous heparin; 5,000 units given before surgery and every 8 hours after surgery until discharge), compared to IPCs alone, for RP for prostate cancer:

1. Prevent the occurrence of symptomatic VTE following surgery? (primary efficacy outcome)
2. Increase the incidence of clinically significant lymphocele? (primary safety outcome)
3. Increase the incidence of clinically significant hematoma? (primary safety outcome)
4. Increase the incidence of major bleeding following surgery? (primary safety outcome)
5. Prevent the occurrence of any VTE (asymptomatic or symptomatic) following surgery? (secondary outcome)
6. Increase estimated blood loss during surgery? (secondary outcome)
7. Increase surgical drain output after surgery? (secondary outcome)

8. Lead to potential surveillance bias measured by increased or decreased use of diagnostic imaging for VTE relative to symptoms (e.g. lower extremity Duplex ultrasound, spiral CT angiography, V/Q scan, etc.)? (secondary outcome)

3. Background (briefly describe pre-clinical and clinical data, current experience with procedures, drug or device, and any other relevant information to justify the research)

An estimated 180,000 new cases of prostate cancer were diagnosed in 2016, and about 90,000 radical prostatectomies are performed in the United States annually [1-3]. Since the year 2000, a sharp change in practice patterns has shifted the traditionally open radical prostatectomy (RP) procedure to current practice where the great majority (likely >70%) are robotic-assisted laparoscopic RPs (RALRP) [3]. According to most guidelines, undergoing RP by any approach classifies a patient as high-risk for venous thromboembolism (VTE), including deep venous thrombosis (DVT) and pulmonary embolism (PE), and would lead to implementation of appropriate intermittent mechanical pneumatic compression devices (IPCs) and pharmacologic prophylaxis [4-8].

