Urologists will initially be blinded to patient randomization and the administration of the preoperative subcutaneous heparin dose to prevent bias on recorded estimated blood loss during the surgery. Postoperatively, administration of subcutaneous heparin will be unblinded during the patient's inpatient stay. Control patients will receive IPCs only and no placebo doses will be administered during their hospital stay. Data analysis will be blinded as to treatment group. Performance and interpretation of lower extremity Duplex screening ultrasound will be blinded to patient randomization. Surveillance bias will be assessed by differential performance of postoperative imaging as described above.

- d. Justification of why participants will not receive routine care or will have current therapy stopped.

All patients will receive routine care. Both arms include patients receiving accepted standards of care.

- e. Justification for inclusion of a placebo or non-treatment group.

The control group in this trial is the group receiving current routine practice at Johns Hopkins with IPCs. The experimental group is the group receiving pharmacologic VTE prophylaxis as practiced at other centers and recommended by most VTE guidelines for major surgery.

- f. Definition of treatment failure or participant removal criteria.

Participants will be removed from the trial if surgery is canceled or not completed for any reason. All patients assigned to the experimental and control arms completing surgery will be included in the study regardless of compliance with pharmacologic prophylaxis doses in an intention-to-treat (ITT) analysis. Patients experiencing an adverse event will be provided appropriate care. Additional per-protocol analyses will be conducted to compare outcomes by compliance with assigned regimen. Patients diagnosed with VTE events will be recommended to obtain routine care locally or at Johns Hopkins per patient preference.

- g. Description of what happens to participants receiving therapy when study ends or if a participant's participation in the study ends prematurely.

Perioperative pharmacologic prophylaxis is only given during the patient's inpatient stay. As mentioned above, all patients will be included in an ITT analysis as possible if they undergo surgery. No planned outcomes will be tracked after the 30-day post-surgical outcomes unless the patient initiates contact.

5. Inclusion/Exclusion Criteria

Inclusion:

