The primary efficacy outcome will be the incidence of symptomatic VTE within 30 days after surgery. A symptomatic VTE event will be defined as any imaging-confirmed VTE diagnosed after evaluation for VTE prompted by the presence of signs/symptoms concerning for VTE. The primary analysis will compare this rate between treatment arms at the 30-day follow-up for all patients. Symptomatic VTE will also include any deaths attributed to a clinically suspected VTE event without imaging confirmation (if autopsy is performed, VTE must be confirmed at autopsy; if autopsy is not performed, clinical suspicion of VTE as the cause will suffice). Symptoms prompting evaluation include:

1. Persistent unilateral or bilateral lower extremity edema
2. Persistent calf pain or cramping
3. Persistent or new chest pain
4. Persistent or new shortness of breath that started suddenly or worsens with exertion
5. Productive cough with bloody sputum
6. Fever and/or tachycardia without any known source of infection
7. Any other clinical concern for DVT or PE

The primary safety outcomes will include three separate measures of incidence of symptomatic lymphocele, incidence of symptomatic hematoma, or major bleeding within 30 days after surgery. Symptomatic lymphocele and symptomatic hematoma will include imaging confirmed events based on imaging pursued at the discretion of the primary attending urologist per routine practice (current routine practice involves imaging only if clinical symptoms suggest possibility of a lymphocele or hematoma). Events will be recorded regardless of the need for intervention (e.g. drain placement by interventional radiology). While screening studies show rates of 25-50% for postoperative lymphocele regardless of surgical approach (open or robotic), the rate of symptomatic lymphocele is thought to be around 10% or less [31,32]. Major bleeding will be defined as the need for transfusion of ≥ 2 units of packed red blood cells after the completion of surgery for anemia attributed to postoperative bleeding or need to return to the operating room for active bleeding.

c. Secondary outcome variables.

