Additional subanalyses (both ITT and per protocol) will be performed with stratification by arm compliance (proportion of scheduled subcutaneous heparin doses administered), performance of pelvic lymphadenectomy (including number of nodes removed), performance of open or robotic surgery (including differences in operative time), and other demographic and comorbidity criteria (including history of VTE, cancer, and other risk factors included in the Caprini Score) to identify patients at highest risk for VTE. Surveillance bias will also be evaluated, as mentioned above, by the differential performance of diagnostic imaging.

e. Interim Analyses.

Two interim analyses of the primary endpoint are planned with potential early stopping for efficacy or futility. O'Brien-Fleming boundaries were used, as implemented in PASS v. 11 (NCSS Software, Inc., Kaysville, UT). The total sample size needed for 82% power with a 1-sided test is 666 (333 per treatment arm), based on 2000 simulations. The interim analyses will be conducted after 1/3 and 2/3 of patients are enrolled (222 and 444, respectively). Alpha-spending at the 2 interim analyses and final analysis is .001,

.015, and .033 (cumulative alpha spent .001, .015, .048), respectively. The futility boundaries at the 1st and 2nd interim analyses, and final analysis are $p=0.816$, 0.272 , and 0.070 , respectively.

At each interim analysis the rates of the 3 safety endpoints (lymphocele, major bleeding, and hematoma) will also be evaluated and 95% confidence intervals calculated. Unacceptable rates for these endpoints are $\geq 15\%$, $\geq 5\%$, and $\geq 10\%$, respectively. If lower 95% confidence bounds meet or exceed these unacceptable rates the trial will be halted for further review and consideration of early stopping.

8. Risks

- a. Medical risks, listing all procedures, their major and minor risks and expected frequency.

Administration of subcutaneous heparin:

1. Major risks:

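### Aim 8 defines surveillance bias as VTE imaging relative to symptoms, but the analysis compares raw imaging counts, so a working drug can look like bias and real bias can be hidden

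*Combined protocol and SAP*

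**What the plan says.** Section 2, aim 8, sets the question as surveillance bias "measured by increased or decreased use of diagnostic imaging for VTE relative to symptoms", and gives leg Duplex, CT angiography and V/Q scanning as examples.

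None of the later sections carries the symptom term:

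- Section 4c: "Surveillance bias will be assessed by differential performance of postoperative imaging as described above".
- Section 7c: "Surveillance bias will be determined by recording the type and frequency of postoperative imaging performed while a patient is in the hospital", or after discharge up to day 30.
- Section 7d, among the continuous secondary endpoints: "number of imaging tests (surveillance bias" is how the variable is named). These endpoints "will be compared in univariate fashion using t-test or Wilcoxon ranksum, and adjusted analyses will use linear regression".
- Section 7d, additional subanalyses: "Surveillance bias will also be evaluated, as mentioned above, by the differential performance of diagnostic imaging".

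Adjustment in section 7d is for confounders that randomisation leaves unbalanced; symptoms are not named. Sections 4a and 7b list seven prompting symptoms. Section 4a has the 30-day call document VTE episodes and their treatment, but does not say that symptoms are recorded for patients without a confirmed VTE.

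**The concern.** Section 7b defines the primary event as "any imaging-confirmed VTE diagnosed after evaluation for VTE prompted by the presence of signs/symptoms concerning for VTE", with an exception for deaths attributed to VTE without imaging. Nearly every primary event therefore brings at least one imaging test with it. If heparin prevents symptomatic VTE, it also removes the tests that those events would have triggered, and the raw count falls on heparin even if clinicians treat identical symptoms identically in both arms. Aim 8 counts decreased use as bias, so the drug's benefit and the bias point the same way on this measure.

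This matters because heparin is unblinded after surgery, there is no placebo, and the primary outcome depends on who is worked up. If clinicians were slower to investigate patients known to be on heparin, VTE would be under-detected in that arm. The raw count would fall just as it does when the drug works, and the analysis could not tell the two apart.

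**Working it through.** **Inputs from the documents.** Symptomatic VTE 5% versus 1.5% and 333 patients per arm (section 7d); a screening subcohort of 200, stratified at randomisation, so about 100 per arm (sections 4a and 7a).

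**Inputs assumed.** The share b of patients worked up for VTE symptoms with a negative result is not in the documents; 5%, 10% and 15% are used, with 0% to 30% as a wider check. The plan gives no significance level for this outcome; two-sided 0.05 is used because aim 8 asks about either direction.

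**Reproducing the plan's figure.** The documents give no figure for the imaging outcome. For the design around it, 333 per arm at 5% versus 1.5%, one-sided 0.05, gives 81.8% power with a fixed sample. Simulation with the two interim looks, nominal cut-offs of 0.001, 0.015 and 0.048, and the interim futility limits gives 82.5%. The plan states 82%, so the inputs are sound.

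**Step 1: imaging removed by the drug alone.** 333 × 0.05 = 16.7 and 333 × 0.015 = 5.0 patients imaged because of VTE. Heparin has about 11.7 fewer imaged patients per arm with no bias.

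**Step 2: false signal when only VTE work-ups count.** Proportion imaged is 0.05 + b versus 0.015 + b, with the same b in both arms. The rejection probability is exact, for the chi-squared test without continuity correction.

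| b | Control | Heparin | Ratio | Chance of p < 0.05 |
|---|---|---|---|---|
| 5% | 10% | 6.5% | 1.54 | 37% |
| 10% | 15% | 11.5% | 1.30 | 26% |
| 15% | 20% | 16.5% | 1.21 | 22% |

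Simulating the planned Wilcoxon test with one test per work-up, and applying b only to patients without VTE, gives 33%, 23% and 17%. Over the wider range the chance runs from 73% at b = 0% to 10% at b = 30%, against a nominal 5%.

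**Step 3: counting the screening Duplex as well.** Add one scan to 100 patients in each arm. At b = 10% the mean difference stays 0.035. Without scans the average variance is (0.15 × 0.85 + 0.115 × 0.885)/2 = 0.115, so the standard error is √(2 × 0.115/333) = 0.026 and z is about 1.33. The scans add 0.30 × 0.70 = 0.21 to the variance, the standard error becomes √(2 × 0.325/333) = 0.044, and z falls to about 0.79. Simulated rejection by t-test and Wilcoxon over b = 5% to 15% is about 0.4% to 3%. This is below 5% because the scans are balanced by design while the unadjusted tests treat them as noise.

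**Step 4: hiding real bias.** Let VTE-negative imaging on heparin be k times that in controls, with b applied to patients without VTE. Totals are equal when k = (0.05 + 0.95b − 0.015)/(0.985b). This gives k = 1.68, 1.32 and 1.20 for b = 5%, 10% and 15%. The test then rejects only about 5% of the time, although VTE-negative imaging differs by 20% to 68%.

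**The case against.** The best defence is that the plan can be read narrowly. Aim 8 specifies imaging for VTE, section 7c records the type of test, and sections 4a and 7c list the screening ultrasound apart from postoperative diagnostic imaging. A VTE-only count without the study scan could then be built from planned data. That stands as a possible reading, but section 7d does not state it, and it still leaves no symptom denominator.

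Three stronger readings are tempting, and the documents do not support them.

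- A reader might infer that an effective drug *will* register as surveillance bias. At work-up rates of 5% or more a significant result is the minority outcome, and if screening scans are counted it nearly disappears. Lymphocele or hematoma imaging could also rise on heparin and offset the fall. Only *can* is supported.
- A reader might infer that this is the plan's only check on detection bias. It is not: the subcohort has a day-30 Duplex regardless of symptoms, performed and read blind to arm (sections 4a and 4c), and the 30-day call is the same in both arms. That check is optional and smaller, but it does not depend on unblinded clinicians' decisions to image.
- A reader might infer that the imaging data are useless. More VTE imaging on heparin, or a shortfall well beyond 3.5 per 100, would still be informative.

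It is also fair that patients with symptoms are a post-randomisation subset, reported open label, so the repaired comparison has limits of its own.

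**Conclusion.** The point holds: the analysis does not answer aim 8. The aim conditions on symptoms and on VTE-directed imaging; the analysis does neither, and the data for the symptom denominator are not clearly collected.

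Its size depends on two things the documents leave open, the VTE-negative work-up rate and what is counted. With VTE work-ups only and an assumed rate of 5% to 15%, a false signal appears in about 37% to 22% of trials at the plan's own effect. With the screening scans included it appears in about 0.4% to 3%, and the fault becomes low sensitivity. Under either count, neither a difference nor its absence can by itself be read as evidence about surveillance bias.

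This is a secondary outcome. The primary test, the sample size and the success criterion are unaffected. It should be corrected before data collection, because symptoms in patients without VTE cannot be reliably reconstructed later.

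**What to change.** - At the existing 30-day call, record the seven listed symptoms for every patient in both arms, whether or not VTE was diagnosed.
- In sections 7c and 7d, define the measure as VTE-directed imaging in hospital or within 30 days, and exclude the protocol screening Duplex.
- Report by arm, with confidence intervals, the proportion imaged among patients with at least one listed symptom and among those with none. Keep the raw count as descriptive.
- Do not use the proportion of positive tests as a bias measure, since it also falls when the drug works. With no bias it is 0.05/(0.05 + b) versus 0.015/(0.015 + b): 50% versus 23%, 33% versus 13%, and 25% versus 9% for b = 5%, 10% and 15%.

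The cost is a short checklist in a call that is already planned and a rewritten analysis paragraph. The downside is small: the symptom-based comparison uses fewer patients and conditions on open-label, post-randomisation reports, so it should be labelled descriptive and read alongside the blinded subcohort Duplex.
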